Low-Intensity Focused Ultrasound Pulsation for Treatment of Motor Deficits in Parkinson's Disease

NCT04593875

October 16, 2022

APPROACH

Participants. Participants will consist of 30 adults, aged 18 to 85 years, diagnosed with Parkinson's Disease (PD).

Subject Recruitment. Subjects will be recruited using flyers and brochures distributed physically and online, as well as from the UCLA Movement Disorder Program in collaboration with [name], MD, PhD. A subpage on the Staglin IMHRO Center for Cognitive Neuroscience (henceforth CCN) website will include study information and an interest form to submit contact information if interested. Recruitment mailers will be distributed to doctor's offices and clinics, where patients (or their doctor's office, upon patient's request) can mail us their contact information if interested in the study.

Screening. Participants will be contacted by study staff who will conduct a telephone screening to ensure eligibility and suitability for MRI.

fMRI Validated LIFUP stimulation. We will use a Brainsonix ultrasound system with a transducer that fits in the 20-channel head coil. Participants will have the low-intensity focused ultrasound pulsation (LIFUP) transducer approximately aimed at the internal globus pallidus (GPI) using skin surface fiducials and gently strapped in place to their head. To minimize the ultrasound energy's exposure to air, a gel pad will be placed between the transducer and the participant's scalp. Participants will then be placed into the scanner where head scout scans will be used to guide more precise targeting adjustments. Once targeting is complete, a T1 image will verify the position of the LIFUP transducer and allow for estimation of the spatial location of the sonication beam focus (approximately 5mm long x 7mm diameter). Participants will receive active sonication at one visit and sham sonication at the other, the order of which will be randomized and counterbalanced across participants. The sonication protocol will consist of 20 ultrasound sonifications in a 30 s ON, 30 s OFF fashion at 650KHz, $Ispta \leq 720 \text{ mW/cm}^2$, 5% duty cycle, 0.5ms pulse width, 73.15mvP-P amplitude, and 100Hz pulse repetition frequency. For sham sonication, the gel pad will block close to all of the ultrasound energy from the transducer. For active sonication, the gel pad will allow the ultrasound energy to pass through. These gel pads are identical in appearance. Resting state fMRI (rs-fMRI) will be collected simultaneously with LIFUP (or sham) sonication.

MRI Data Acquisition: We will use a 3-Tesla Siemens PRISMA scanner. We will collect high-resolution 0.8 mm^3 T1-weighted images, pseudo-continuous arterial spin labeling (PCASL) images, and rs-fMRI images. Total time in the scanner will be approximately 75 minutes each session.

Analysis and Publications. MRI data analysis will begin immediately during data collection, as structural and functional MRI are used to ensure successful targeting of LIFUP sonication. Group level analysis will occur after data from 30 subjects have been collected.

This project has four main aims:

#1: Validate basal ganglia-thalamocortical (BGTC) network perfusion and resting state functional connectivity (rs-FC) is associated with Parkinson's Disease (PD) deficits in cognition and motor impairments.

#2: Use LIFUP to modulate neural activity in the GPI, and PCASL pre- and post- LIFUP to assess up-regulation of BGTC network perfusion.

#3: Measure BGTC network rs-FC before, during, and after LIFUP stimulation.

#4: Assess potential LIFUP-related changes in motor function and their association with changes in perfusion and rs-FC.

PROCEDURES

MRI Analysis. Preprocessing and analyses will be performed using FSL Version 6.0 (www.fmrib.ox.ac.uk/fsl). Structural data will be linearly registered to the standard MNI152 T1 2mm brain. Processing of fMRI data will include correcting for motion artifacts (using framewise displacement, DVARS, within-subject independent component analysis, and outlier removal),

slice timing correction, high-pass temporal filtering ($t > 0.01$ Hz) unwarping, and spatial smoothing (Gaussian Kernel FWHM = 8mm). Functional data will be linearly registered to stereotaxic MNI space and co-registered with anatomic data for each participant. Subjects with greater than 0.5mm mean framewise displacement will be excluded from analyses. PCASL scans will be transferred to MNI space using non-linear registration in FSL and then linearly registered with anatomic data for each participant.

Stimulation-related fMRI. rs-fMRI will be collected continuously during the LIFUP stimulation paradigms. A block-design model will be used to statistically compare the blood oxygenation level dependent (BOLD) signal during LIFUP stimulation blocks to the BOLD signal during no-stimulation blocks. To examine LIFUP-related network connectivity, we will use a seed-based approach and examine whole brain connectivity with the LIFUP target of interest⁶⁹ and compare between stimulation (on-off) conditions using psychophysiological interaction modeling (PPI)⁷⁰. We will also use dynamic connectivity to evaluate changes in connectivity across the course of the LIFUP stimulation paradigm.

RS-fMRI. We will compare rs-FC before and after stimulation. Independent component analyses (ICA) will be used to statistically extract functional networks from each participant's rs-fMRI. Dual-regression analysis will then compare resting state networks between baseline and post-LIFUP to determine the effect of LIFUP on resting state functional connectivity. Age, sex and education will be included as additional regressors.

Perfusion. PCASL is an arterial spin labeling technique that measures cerebral blood flow. It produces a perfusion image with voxel values representing local perfusion rates. Within FSL we will perform a voxel-wise repeated measures analysis between the pre-LIFUP and post-LIFUP PCASL scans. By examining the differences between these two scans, we can determine the effects that LIFUP has on perfusion in the target region and other connected regions. We will also perform a repeated measures analysis of perfusion between conditions (LIFUP vs. sham). By examining subjects receiving sham on visit 2, we can compare pre-sham resting state fMRI and PCASL to the pre-LIFUP values at visit one, to determine the persistence of blood flow effects over a 2-week interval. This will suggest how frequently LIFUP would need to be administered during a more comprehensive clinical trial.

Motor Assessment. Subjects will undergo a motor evaluation with assessments of motor symptoms such as a grooved pegboard task, a 15-second recording of forearm and hand tremor, and dynamometer grip strength measurements. They will also complete The Essential Tremor Rating Assessment Scale (TETRAS) and the Unified Parkinson's Disease Rating Scale (UPDRS). The motor testing portion of the UPDRS will be video-recorded for research staff to review after the session in order to maximize rating accuracy. Any recordings containing participants faces will be exclusively stored locally on UCLA-owned devices kept in a locked room; any video transferred off these devices will first be edited to remove faces and any other identifying information. The original footage will be deleted once this editing is complete. Participants will complete all of these assessments both before and after the MRI/LIFUP portion of each session. We will also ask the participant's partner or caregiver to complete part 1 of the TETRAS during the first virtual session. In addition to the measurements taken during the in-person and virtual sessions, we will ask participants to wear a watch-style device called the Personal KinetiGraph (PKG) starting one week prior to their first in-person session and ending one week after their second in-person session. This device provides round-the-clock monitoring of tremor activity and sleep quality. Additionally, immediately after administering LIFUP or sham stimulation, we will be asking participants open-ended questions about any perceived changes.

Psychological Assessment. After giving informed consent, subjects will be evaluated for cognitive status with the Modified Telephone Interview for Cognitive Status (TICS-M). Subjects will undergo a baseline psychological evaluation at their first in-person visit composed of the State Trait Anxiety Inventory (STAI), Beck's Depression Inventory (BDI), the Questionnaire for Impulsive-Compulsive Disorders in Parkinson's Disease–Rating Scale (QUIP-RS), and the REM Sleep Behavior Disorder Screening Questionnaire (RBDSQ). The BDI, the RBDSQ, the "state" portion of the STAI, and an open-ended question about any perceived changes not covered by the inventories will also be completed before MRI/LIFUP at the second in-person session and at both follow-up Zoom sessions. Additionally, the Stanford Sleepiness Scale (SSS) will be completed both before and after each scan session and at each post-LIFUP Zoom session, in

order to control for potential fatigue effects on assessment results. Participants will also be completing a truncated version of the Phenomenology of Consciousness Questionnaire (PCQ) immediately after each scan session, and an experimental probabilistic learning task at each follow-up Zoom session.

STUDY DESIGN

The design is comprised of 2 in-person sessions, a consenting/intake Zoom session, a brief PKG setup Zoom session, 2 post-LIFUP follow-up Zoom sessions, 4 brief follow-up phone calls, and 4 weeks of round-the-clock PKG data collection. All in-person sessions will be held in private rooms on the C-level of the Semel Institute at UCLA, with scans taking place at CCN. All virtual sessions will take place over UCLAHealth HIPAA-secure Zoom. Staff will conduct all Zoom calls and phone calls from private locations to ensure participant confidentiality.

Design Overview

- Pre-screening: upon first contact by the participant, we will conduct an initial screening aimed at ensuring the participant meets inclusion criteria.
- During the intake Zoom session, we will conduct remote consenting procedures and MRI safety screening, and collect data necessary for PKG setup.
- During the remote PKG setup session, we will obtain a Zoom recording of the participant putting on the PKG device and familiarize the participant with the usage of the device.
- During in-person session #1 we will conduct consent procedures, pre-LIFUP behavioral and motor testing, MRI, either LIFUP or sham stimulation during the MRI, and post-LIFUP motor testing.
- During in-person session #2 (two weeks after in-person session #1), we will administer pre-LIFUP behavioral and motor testing, MRI, either LIFUP or sham stimulation (whichever was not received during the first session), and post-LIFUP motor testing.
- 48-72 hours after each in-person session, behavioral testing will be administered, as well as motor testing that can be conducted remotely.
- 4 and 7 days after each in-person session, a brief follow-up call will be conducted.
- Participants will be wearing the PKG device round-the-clock from one week prior to the first in-person session until one week after the second in-person session.
- The independent variable is the type of LIFUP modulation we will perform: active stimulation vs. sham stimulation.
- The dependent variables are: resting-state functional connectivity, perfusion, severity of motor symptoms, severity of psychological symptoms, and performance on the probabilistic learning task.

Detailed Design

Pre-screen: when we are put in contact with a potential participant, we will ask them to undergo a brief screening over the phone. The purpose of this session is exclusively to determine eligibility with respect to the following inclusion and exclusion criteria:

- **Inclusion Criteria:** (i) diagnosis of PD, (ii) age 18-85, (iii) fluent in English, (iv) hearing and vision normal or corrected-to-normal, and (v) willing and able to provide informed consent
- **Exclusion Criteria:** (i) mobility issues requiring use of a wheelchair or walker, (ii) significant cognitive impairment, (iii) history of neurological disorder other than Parkinson's, (iv) history of psychiatric disorders other than sleep disorders, anxiety disorders, and major depressive disorder, (v) pre-PD history of sleep disorders, anxiety disorders, and/or major depressive disorder, (vi) contraindication to MRI, (vii) medication changes within past 6 weeks or planned changes in next 6 weeks, (viii) pregnant or planning to become pregnant, (ix) history of medical event(s) likely to result in neurological abnormalities, (x) uncontrolled diabetes or hypertension, (xi) diagnosis of severe lung, liver, heart, or kidney disease, (xii) history of alcohol or substance abuse (other than nicotine or caffeine)

The only data that will be retained about this screen is whether the participant is currently eligible, ineligible, or eligible at some future date, as well as their necessary contact information and any information necessary to verify MRI safety. No other record will be kept of the contents of the potential participant's answers.

Remote Session 1 [90 minutes]

The aim of this session is to (a) complete informed consent procedures, (b) evaluate cognitive status via the TICS-M (c) complete MRI safety screening procedures, (d) obtain participant demographic and medication information, (e) have caretaker complete part 1 of the TETRAS, and (f) schedule all other sessions

Remote PKG Setup Session [approx. 10 minutes]

The aim of this session is to (a) obtain a recording of the participant putting on the PKG device to ensure correct setup and (b) familiarize the participant with the usage of the device. Participant faces and voices will be removed from recordings before they are transferred from UCLA-owned devices to the UCLAHealth Box server. The PKG device will be worn from one week prior to the first in-person session to one week after the second in-person session. To collect continuous tremor data, the PKG device is to be worn round-the-clock, except for when participant is swimming, showering, syncing the device weekly, or in a LIFUP/MRI session.

In-Person Session 1 [approx. 4.5 hours]

This session will take place one week after the PKG setup session. The aim of this session is to (a) complete pre-LIFUP motor assessments (UPDRS, TETRAS, 1-minute forearm recording, grip strength and grooved pegboard tasks), (b) complete pre-LIFUP psychological assessments (SSS, STAI, RBDSQ, QUIP-RS, BDI), (c) perform neuronavigation-guided LIFUP or sham stimulation during rsfMRI, (d) collect information on any perceived changes immediately post-LIFUP, (e) collect pre-LIFUP high res T1w, PCASL, and rsfMRI scans and post-LIFUP PCASL and rsfMRI scans, (f) complete post-LIFUP motor assessments (UPDRS part 3, TETRAS part 2, grip strength and grooved pegboard tasks), and (g) complete post-LIFUP psychological assessments (SSS, PCQ).

Post-LIFUP Remote Session 1 [60 minutes]

This session will take place 48-72 hours after the first in-person session. The aim of this session is to (a) complete post-LIFUP motor assessments that can be administered remotely (UPDRS parts 1, 2, and 4, TETRAS part 1), (b) complete post-LIFUP psychological assessments (SSS, BDI, RBDSQ, STAI-State, probabilistic learning task), and (c) collect information on any perceived changes not covered in the motor and psychological assessments.

In-Person Session 2 [approx. 4 hours]

This session will take place two weeks after the first in-person session. The aim of this session is to (a) complete pre-LIFUP motor assessments (UPDRS, TETRAS, 1-minute forearm recording, grip strength and grooved pegboard tasks), (b) complete pre-LIFUP psychological assessments (SSS, STAI-State, RBDSQ, BDI), (c) perform neuronavigation-guided LIFUP or sham stimulation during rsfMRI, (d) collect information on any perceived changes immediately post-LIFUP, (e) collect pre-LIFUP PCASL and rsfMRI scans and post-LIFUP PCASL and rsfMRI scans, (f) complete post-LIFUP motor assessments (UPDRS part 3, TETRAS part 2, grip strength and grooved pegboard tasks), and (g) complete post-LIFUP psychological assessments (SSS, PCQ).

Post-LIFUP Remote Session 2 [60 minutes]

This session will take place 48-72 hours after the first in-person session. The aim of this session is to (a) complete post-LIFUP motor assessments that can be administered remotely (UPDRS parts 1, 2, and 4, TETRAS part 1), (b) complete post-LIFUP psychological assessments (SSS,

BDI, RBDSQ, STAI-State, probabilistic learning task), and (c) collect information on any perceived changes not covered in the motor and psychological assessments.

Four-day Post-LIFUP Follow-Up Calls [approx. 5 min each]

These calls will take place four days after each in-person session. The aim of these calls is to collect information on any perceived changes since the LIFUP session or the post-LIFUP Zoom session.

One-week Post-LIFUP Follow-Up Call 1 [approx. 10 min]

This call will take place seven days after the first in-person session. The aim of these calls is to (a) collect information on any perceived changes since the LIFUP session or prior follow-up sessions, and (b) walk the participant through the process of syncing the PKG device in order to ensure successful data transfer.

One-week Post-LIFUP Follow-Up Call 2 [approx. 10 min]

These calls will take place seven days after each in-person session. The aim of these calls is to (a) collect information on any perceived changes since the LIFUP session or prior follow-up sessions, and (b) walk the participant through the process of syncing the PKG device in order to ensure successful data transfer, (c) collect feedback on participant experience with the study, and (d) provide instructions for returning the PKG device.

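### T1 and fMRI reach MNI space by a linear transform only and PCASL by a non-linear one with an unclear final space, which may dilute or mislocate local effects near the small GPi target

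*Combined protocol and SAP*

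**What the plan says.** The MRI Analysis paragraph under PROCEDURES gives three registration statements:

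- T1: "Structural data will be linearly registered to the standard MNI152 T1 2mm brain".
- fMRI: "Functional data will be linearly registered to stereotaxic MNI space and co-registered with anatomic data for each participant".
- PCASL: "PCASL scans will be transferred to MNI space using non-linear registration in FSL and then linearly registered with anatomic data for each participant".

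It gives no reason for treating PCASL differently, no non-linear step for T1 or fMRI, no rule for the space in which modalities are combined, and no alignment check in template space. An 8 mm FWHM Gaussian kernel is listed among the fMRI processing steps. No smoothing is stated for PCASL.

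Three other places matter:

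- The section on fMRI-validated LIFUP stimulation puts the beam focus at "approximately 5mm long x 7mm diameter" and says its location is estimated from a T1 image of each participant.
- The Stimulation-related fMRI paragraph says "we will use a seed-based approach and examine whole brain connectivity with the LIFUP target of interest". It does not say whether that seed is defined in native or template space.
- The Perfusion paragraph plans voxel-wise repeated-measures tests, read in the target and in connected regions.

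Aim 1 relates perfusion and rs-FC in the basal ganglia-thalamocortical network to PD deficits. Aim 4 relates motor change to change in each of the two imaging measures.

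**The concern.** A linear transform adjusts position, orientation, size and shear for the whole brain. It cannot follow local differences such as ventricle size, which shift the deep nuclei. With ages from 18 to 85 those differences may be considerable, and the target is a few millimetres across.

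Two consequences follow if the plan is carried out as written:

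1. **Between participants.** The same MNI voxel may be GPi in one person's fMRI map and neighbouring tissue in another's. A local effect is then spread out in the group map and its peak falls.
2. **Between modalities.** If one template region is used to extract both perfusion and connectivity, it may cover different tissue in each, because the two were brought to MNI by different transforms. The extracted values carry extra noise, and their associations with motor measures weaken.

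The PCASL sentence adds a separate difficulty. Read in order, it places the images in MNI space and then registers them to the participant's anatomy, so a reader cannot tell which space the voxel-wise perfusion analysis uses.

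With 30 participants, a weakened result at the target could be taken as absence of a LIFUP effect when part of the cause is the processing.

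**Working it through.** The plan states no registration accuracy, so there is no figure of its own to reproduce. The calculation below shows only how sensitive a focus of this size is to misalignment.

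**Inputs from the documents**
- Focus: length 5 mm, diameter 7 mm (section on fMRI-validated LIFUP stimulation).
- fMRI smoothing: 8 mm FWHM (MRI Analysis).

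**Assumptions**
- The effect is uniform over a cylinder of those dimensions and zero elsewhere.
- Misalignment between participants is Gaussian and independent on each axis, with SD s of 1, 1.5, 2 or 2.5 mm. The documents give no value.

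**Step 1: the kernel as an SD.** σk = 8 / √(8 ln 2) = 8 / 2.3548 = 3.397 mm, so σk² = 11.54 mm².

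**Step 2: add misalignment.** Averaging over random offsets acts as further Gaussian blurring, so σ² = 11.54 + s².

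**Step 3: height at the centre of the blurred cylinder.**
P(σ) = [1 − exp(−3.5² / (2σ²))] × erf(2.5 / (σ√2))

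With s = 0: P = 0.4118 × 0.5382 = 0.2216. Smoothing alone thus leaves about 22% of the unsmoothed height, before any misalignment.

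**Step 4: height relative to perfect alignment.** The mean 3-D offset is s√(8/π).

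| s per axis (mm) | Mean offset (mm) | σ² | Radial term | Axial term | P | P / 0.2216 |
|---|---|---|---|---|---|---|
| 1 | 1.6 | 12.54 | 0.3864 | 0.5198 | 0.2008 | 0.91 |
| 1.5 | 2.4 | 13.79 | 0.3586 | 0.4992 | 0.1790 | 0.81 |
| 2 | 3.2 | 15.54 | 0.3257 | 0.4740 | 0.1544 | 0.70 |
| 2.5 | 4.0 | 17.79 | 0.2913 | 0.4466 | 0.1301 | 0.59 |

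The loss of peak height is therefore about 9% to 41% over the assumed range.

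**Step 5: what a non-linear warp could recover.** It leaves error of its own, so the gain is the difference between two rows and not the whole loss. If it reduced s from 2 to 1.5 mm, the relative peak would rise from 0.70 to 0.81; from 2 to 1 mm, from 0.70 to 0.91. The documents do not say which reduction, if any, would be achieved.

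**The case against.** The strongest reply is that the text supports a request for clarification and little more. Its parts, taken in turn:

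- **No error is shown.** A reader might infer that the GPi is in fact poorly aligned. The documents give no residual error for either method, so only a risk can be stated. This stands.
- **Aim 4 does not correlate the modalities.** A reader might infer a voxel-by-voxel relation between perfusion and connectivity. The aim relates motor change to each imaging measure. The mismatch between modalities matters only where one template region serves both, which the plan neither states nor excludes. This stands.
- **Aim 2 is not the exposed aim.** Its outcome is PCASL perfusion, which already has a non-linear step. The linear transform of T1 and fMRI does not show dilution there. This stands; for PCASL only the unclear final space remains.
- **Raw overlap overstates the loss.** Without smoothing, the shifted cylinder overlaps its intended position by about 65%, 51%, 39% and 29% for the four SDs. It is tempting to read these as the shrinkage of the group effect. They ignore the 8 mm kernel on the modality that is registered linearly, and they are not the difference between linear and non-linear registration.
- **The LIFUP contrasts are within participant.** A stable misalignment is common to the scans being compared, so it dilutes or displaces an effect and does not produce one. This stands for pre/post and LIFUP/sham. Aim 1 is an association across participants, so the pairing does not cover it; only weakening is claimed there.
- **Much of the plan works at network scale.** Dual regression on ICA networks depends less on a few millimetres than a seed at the focus does. A seed placed on each participant's own T1 would not be moved by template error. Both are fair, but the plan does not say that the seed is native, and a native seed would not align the group maps.
- **The PCASL sentence can be read kindly.** Because T1 is itself taken to MNI, the linear step may take place within MNI space. That is possible, which is why the point is ambiguity and not a proven mistake.

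**Conclusion.** The point holds as a risk that the plan leaves open, and it is cheap to remove. T1 and fMRI reach MNI by a linear transform and PCASL by a non-linear one, without explanation, and the final space of the perfusion images is unclear. The consequence is possible dilution or mislocation of a local effect in group fMRI maps (Aim 3), and possible weakening of region-based associations of deficits or motor change with perfusion and rs-FC (Aims 1 and 4).

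The size rests on an assumed misalignment. For SDs of 1 to 2.5 mm per axis, the smoothed group fMRI peak falls to between 0.91 and 0.59 of its value under perfect alignment, and only part of that is recoverable. The figures also assume a uniform effect confined to the stated focus; a more extended effect would lose less. The documents do not support saying that alignment is known to be poor, that the LIFUP contrasts are biased towards a false effect, or that the Aim 2 perfusion result is diluted by the linear step. The change is worth making but is not critical to the trial.

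**What to change.** Replace the three registration sentences under MRI Analysis with one chain for all modalities:

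1. Register fMRI and PCASL to the participant's own T1 (rigid or boundary-based).
2. Register T1 to MNI152 with the FSL non-linear tool.
3. Concatenate the transforms and apply them once, with the same T1-to-MNI warp for fMRI and PCASL.
4. Check alignment visually at the GPi for each participant.

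State that group voxel-wise analyses are done in MNI space. Define the LIFUP-target seed or region from the focus estimated on each participant's own T1, and use that same region for both modalities.

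The cost is some processing time and the checking of warps for 30 participants. FSL is already the named software, non-linear registration is already planned for PCASL, and no new data are needed.

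### Must the 0.5 mm head-motion exclusion be rewritten because it does not name the analyses or scans it covers?

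*Combined protocol and SAP*

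**What the plan says.** Under PROCEDURES, the MRI Analysis section opens with "Preprocessing and analyses will be performed using FSL Version 6.0". It then lists the fMRI processing steps, naming framewise displacement among the tools for correcting motion, and describes registration of the functional data. The rule follows: "Subjects with greater than 0.5mm mean framewise displacement will be excluded from analyses". The next sentence turns to another modality: "PCASL scans will be transferred to MNI space using non-linear registration in FSL".

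The rule counts subjects, not runs or visits, and does not qualify the word analyses. Resting-state fMRI is taken at several points, since Aim 3 is to "Measure BGTC network rs-FC before, during, and after LIFUP stimulation". In-Person Session 1 is to "collect pre-LIFUP high res T1w, PCASL, and rsfMRI scans and post-LIFUP PCASL and rsfMRI scans", and In-Person Session 2 repeats the pre and post scans. The Perfusion section has its own analysis: "Within FSL we will perform a voxel-wise repeated measures analysis between the pre-LIFUP and post-LIFUP PCASL scans". Motor Assessment and Psychological Assessment are separate sections, and neither mentions head motion. Under Analysis and Publications, "Group level analysis will occur after data from 30 subjects have been collected". No replacement of participants excluded for motion is described.

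**The concern.** Two details needed to apply the rule are not written down: the analyses it governs and the scans that are averaged.

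Perfusion is measured by PCASL in separate acquisitions, also analysed in FSL. If the rule covers all FSL work, a participant who moved during an fMRI run would leave the perfusion analysis (Aim 2) even if the PCASL scans were good. That participant would also leave the perfusion part of Aim 4, which is to "Assess potential LIFUP-related changes in motor function and their association with changes in perfusion and rs-FC". Taken without its section heading, the sentence would remove the motor, wearable-device and psychological data as well.

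The averaging question has practical consequences. One person can pass or fail according to whether the mean is taken per run, per visit or over everything, and that choice could be made after motion is known. If head motion rises with motor severity, which is plausible in Parkinson's disease but is an assumption here, the analysed sample would also be milder than the enrolled one.

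**Working it through.** The plan states no exclusion rate, power, significance level or effect size, so it has no figure to reproduce. The check has a textual part and an illustrative part.

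**1. Scope, from the text**

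- *Motor, device and psychological data.* The section is headed MRI Analysis, and its opening sentence ties its analyses to FSL. Rating scales, pegboard, grip strength and wearable data are not FSL analyses, and their own sections carry no such rule. This reading fails.
- *PCASL.* Framewise displacement is introduced only for fMRI. The sentence before the rule concerns functional data, and PCASL begins in the sentence after it. The rule therefore reads as the end of the fMRI block. An MRI-wide reading is possible because PCASL falls under the same heading, but it is not the natural one.

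**2. Which scans, from the text**

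Taking each acquisition as one run, there are 3 fMRI runs (pre, during, post) × 2 visits = 6 per participant, and 2 PCASL scans × 2 visits = 4. The averaging choice can change who is excluded. With five runs at an assumed 0.25 mm and one at 0.9 mm, the six-run mean is (5 × 0.25 + 0.9)/6 = 0.36 mm. That participant stays under a six-run mean and goes under a per-run rule.

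**3. How many could be lost (assumed inputs)**

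Assume run motion is normal with between-run correlation 0.7, and that 10% or 20% of runs exceed the limit. On the standardised scale the limit is z = 1.282 or 0.842. The six-run mean has variance 0.7 + 0.3/6 = 0.75, so the share excluded is 1 − Φ(z/√0.75). The either-visit and any-run rows come from simulating 1,000,000 participants.

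| Reading | 10% of runs fail | 20% of runs fail | Of 30 |
|---|---|---|---|
| Six-run mean | 7% | 17% | 2–5 |
| First baseline run only | 10% | 20% | 3–6 |
| Either visit's mean | 10% | 22% | 3–7 |
| Any single run | 26% | 43% | 8–13 |

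The any-run count depends heavily on correlation. At an assumed 5% run failure it is 30 × (1 − 0.95⁶) = 7.9 of 30 with independent runs, and 30 × 0.05 = 1.5 with fully correlated runs.

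**4. Cost in precision**

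The standard error is multiplied by √(30/n):

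- 2 lost: √(30/28) = 1.035
- 6 lost: √(30/24) = 1.118
- 7 lost: √(30/23) = 1.142
- 13 lost (any-run reading at 20%): √(30/17) = 1.328

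For perfusion these are upper figures within each scenario. They treat every excluded participant's PCASL as usable, which the documents do not establish. Power for a single-outcome paired t-test is not used, because the perfusion analysis is voxel-wise.

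**5. Cost in bias**

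- *Active-sham.* The rule removes both periods of a participant together. In a simulation of 2,000,000 participants with no treatment effect and an outcome-to-run-motion correlation of 0.2–0.3, the shift was within 0.004 SD of 0.
- *Pre/post.* In the same simulation the shift was at most 0.016 SD in size, and only when pre scans alone or post scans alone counted.
- *Milder sample.* Under the six-run mean, let k = z/√0.75. Severity among those retained shifts by −(ρ/√0.75) × φ(k)/Φ(k), where ρ is the correlation of severity with single-run motion. This is 0 at ρ = 0, and −0.08 SD (10% failing) or −0.17 SD (20%) at ρ = 0.5. It affects generalisability. It biases the effect estimate only if benefit varies with severity.

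**The case for a change.** The strongest case for a change is that the rule cannot be applied reproducibly as written. Even if fMRI was meant, the scans to be averaged are not named, and the table shows that the number excluded depends on that choice. Analysts who already know the motion values would have freedom that one sentence could remove. PCASL shares the heading and the software, has no motion criterion of its own and is not exempted, so the wider reading is not fanciful.

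The Perfusion section also compares visits among those who receive sham second, about 15 people if the order is balanced. There, one loss raises the standard error by √(15/14) − 1 = 3.5%, against √(30/29) − 1 = 1.7% in the full sample.

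Part of this stands. The averaging unit is undefined, PCASL is not expressly exempted, and clarification would cost almost nothing. It does not show that the rule gives a wrong answer. In its ordinary sense, applied to the fMRI scans that enter an analysis, excluding high-motion data is sound. The freedom to choose a reading affects mainly precision, since the active-sham contrast shows essentially no bias under no effect. A sensitivity analysis retaining the excluded data, a run-level mixed model, a motion covariate and reporting of exclusions by condition are good practice or preference. They do not repair a faulty rule. A requirement to keep every randomised participant would go further, into missing visits that have nothing to do with head motion.

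**Conclusion.** No change to the plan follows. The wording gap is real but is a missing detail. The heading, the fMRI-only use of framewise displacement and the order of the sentences point to fMRI, and analysts would probably fill in the averaging unit sensibly. The claim that motor, device or psychological data are at risk does not hold. The claim about PCASL is possible but is not the natural reading.

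If the wider reading were adopted, some participants could leave the perfusion analyses because of fMRI motion alone. The number cannot be derived from the documents. Under the averaging readings with assumed 10–20% run failure and correlation 0.7, it is 2–7 of 30, which raises the standard error by 3.5–14%. The any-run reading costs more, up to 33% in that scenario, but for perfusion it requires two less natural readings at once. Simulated bias with no treatment effect is about 0 for active-sham and at most 0.02 SD for pre/post.

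The conclusion rests on reading the rule within its section and on the assumptions stated above. It would need revisiting if the sponsor did intend the rule to cover all imaging or all outcomes.
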